8.3 Population for Analyses

All statistical analyses will be based upon the total cohort of participants randomized into the trial. Although data on some patients may be missing, all relevant data available from each participant will be employed in the analyses. Patients will be included in the treatment group to which they were randomly assigned regardless of compliance.

8.4 Statistical Analyses

8.4.1 General Approach

In general, summaries of categorical data will be presented as number of observations and a percentage. Summaries of continuous data will be presented as means with standard deviation if the variable follows a normal distribution, or else as the median and 95% confidence interval.

Binary or categorical will be reported as a proportion with relative risk and 95% confidence intervals as appropriate. For normally distributed continuous outcomes, least squares means general linear regression will be used to estimate means and 95% confidence intervals. For continuous outcomes that are not normally distributed and cannot be transformed to approximate normality, the Wilcoxon test and the Hodges-Lehmann estimators of the median will be reported.

8.4.2 Analysis of the Primary Endpoint

The primary outcome is continuous and defined as MME consumed inpatient post-cesarean not normally

ELECTRON Protocol # 2022H0046

distributed and cannot be transformed to approximate normality, the Wilcoxon test and the Hodges-Lehmann estimators of the median will be reported. If normally distributed then paired t-test and mean with standard deviations will be reported.

Analysis of Secondary Endpoint

Secondary outcomes that are binary or categorical will be reported as a proportion with relative risk and 95% confidence intervals as appropriate. For normally distributed continuous outcomes, least squares means general linear regression will be used to estimate means and 95% confidence intervals. For continuous outcomes that are not normally distributed and cannot be transformed to approximate normality, the Wilcoxon test and the Hodges-Lehmann estimators of the median will be reported.

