6.3 Concomitant Therapy

Medications for postoperative pain management will be at the discretion of the clinical team. Our institution uses standardized postoperative medication order sets that include oxycodone, acetaminophen and/or ibuprofen.

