8.2 Sample Size Determination

Review of inpatient post-operative data, showed that from post-operative day 0 to 2 our patients consume on average MME 42 with SD 15. For 20% reduction in MME to 33.6 and 90% power would need total sample size of 134. Resulting in 67 intervention group and 67 participants in control group.

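### Section 8.4.2 lets the observed MME distribution choose the primary test and effect measure, with no criterion, so the size of the reduction has no fixed estimand

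*Combined protocol and SAP*

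**What the plan says.** The primary endpoint is total inpatient opioid consumption in MME. Section 8.4.2 gives it two possible analyses.

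- **Non-normal branch:** if MME is not normally "distributed and cannot be transformed to approximate normality, the Wilcoxon test and the Hodges-Lehmann estimators of the median will be reported".
- **Normal branch:** "If normally distributed then paired t-test and mean with standard deviations will be reported".

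Section 8.4.1 sets a different rule for normal data: "For normally distributed continuous outcomes, least squares means general linear regression will be used to estimate means and 95% confidence intervals". Its non-normal rule opens with the same condition as 8.4.2, "For continuous outcomes that are not normally distributed and cannot be transformed to approximate normality", and leads to the same Wilcoxon test. For descriptive summaries of non-normal variables it asks for a mean "or else as the median and 95% confidence interval".

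The sample size in 8.2 rests on means. It says that "our patients consume on average MME 42 with SD 15" over postoperative days 0 to 2, and then: "For 20% reduction in MME to 33.6 and 90% power would need total sample size of 134".

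On dosing, Table 1 in 6.1.1.1 converts oxycodone at 1.5 and hydrocodone at 1. Section 6.3 leaves pain medication to the clinical team and describes "standardized postoperative medication order sets that include oxycodone, acetaminophen and/or ibuprofen".

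**The concern.** Four gaps stand on the face of the text.

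1. No section gives a normality test, a threshold, a list of permitted transformations, or who decides and whether that person is blinded.
2. If a transformation succeeds, neither branch of 8.4.2 applies and no primary analysis is stated.
3. The normal branch of 8.4.2 lists arm means and SDs, with no between-arm difference and no confidence interval. It also disagrees with 8.4.1 on the method. (It names a paired test for two independent arms, which is a separate error.)
4. The branches estimate different things: a difference in means on one, a Hodges-Lehmann (HL) quantity on the other, for which 8.4.2 plans no interval.

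The answer to how much the device reduces MME would therefore be defined only after the outcomes are seen, and a reader could not tell whether the choice was influenced by the result.

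**Working it through.** **Inputs.** From 8.2: control mean 42, device mean 33.6 (difference 8.4), SD 15, 67 per arm, 90% power. From Table 1: oxycodone factor 1.5, hydrocodone factor 1. Assumed, because the plan is silent: two-sided alpha 0.05, distribution shape, 5 mg dose units, and Shapiro-Wilk on residuals as a stand-in normality rule.

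**The plan's own figure.** n per arm = 2 × (1.960 + 1.282)² × 15² / 8.4² = 67.01, so 67 per arm and 134 in total is reproduced (normal-approximation power 0.89995; exact t-test power 0.896). One-sided 0.05 would give 110 in total. The calculation is for a difference in means.

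**How the branch would fall.** Simulations used 67 per arm and 4,000 trials per scenario, with doses on a 7.5 MME grid. With normal-shaped data, Shapiro-Wilk rejects in about half of trials (44-56% across runs). With gamma-shaped data of the same SD it rejects in about 97-98%. Under the plan's own figures the branch can be close to a coin toss.

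**Effect on inference at SD 15.**

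| Quantity | Result |
|---|---|
| t-test and Wilcoxon disagree on significance | about 2-8% of trials |
| Type I error, mechanical pre-test rule | 0.046-0.053 |
| Type I error, smaller p of t-test and Wilcoxon | 0.052-0.069 |
| Same, with a log-scale t-test added | 0.063-0.072 |

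The range for free choice also includes runs with coarser dose steps, SD 10, and many zero values. Disagreement between the tests reaches about 13% with skewed data and SD 30.

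**Tablet steps (conditional).** One 5 mg oxycodone unit is 5 × 1.5 = 7.5 MME. If all inpatient opioid is oxycodone in 5 mg multiples, every between-arm difference is a multiple of 7.5. There are 67 × 67 = 4,489 such differences, an odd number, so their median is itself a multiple of 7.5. At the design effect the HL estimate was a 7.5 MME reduction in 81-87% of trials, 15 in 9-15% and 0 in 4%.

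A rank-based 95% interval for HL had a limit at exactly 0, among trials with Wilcoxon p < 0.05, in:

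- 52-55% at the 20% design effect;
- 75-79% at a 15% effect;
- 88-92% at a 10% effect.

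For example, 0.553 × power 0.874 = 0.48 of all trials at the design effect. If hydrocodone is mixed in (5 × 1 = 5 MME against 7.5), steps become 2.5 MME and the design-effect figure falls to 11-14%. Without a grid it is about 0.

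**Power if one test is fixed.** At the design effect on the 7.5 grid: about 0.89 (mean comparison) versus 0.87 (Wilcoxon) for normal-shaped data, and 0.94 versus 0.93 for gamma-shaped data. With strong skew the direction varies. One gamma case with SD 30 gave 37% versus 56%, against the mean comparison. A zero-inflated case gave 38% versus 33%, in its favour.

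**The case against.** **The practical harm is modest.** A mechanical rule leaves type I error near 5%, free choice adds at most about two points, and N = 134 is little affected. This stands, and it limits the severity. Shapiro-Wilk is also an assumed rule, so the branch frequencies describe one possible procedure and not the plan's.

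**The tablet argument rests on unstated facts.** Section 6.3 leaves drugs to clinical discretion, no tablet strength is given, and Table 1 also lists hydrocodone. This stands, so the 7.5 MME step is conditional. The nearest step also lies only 8.4 - 7.5 = 0.9 MME from the design difference, against a standard error of 15 × √(2/67) = 2.6 MME.

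**The HL wording can be read another way.** It could mean a one-sample estimator in each arm. On that reading the difference between arms moves in steps of 3.75 MME or finer (7.5 in 46% of trials, 11.25 in 31%, 3.75 in 14%). That two readings are possible supports the point that the effect measure is not fixed.

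**Fixing Wilcoxon in advance would equally remove the data-driven choice.** True. The argument for means is consistency with 8.2. The objective and hypotheses speak of consumption or amount and do not say mean, so they do not settle it.

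**A reader might infer that the HL estimate contradicts its own p-value.** The documents do not support that. At SD 15 on the 7.5 grid, an HL estimate of 0 with p < 0.05 never occurred, and 0 was never inside the interval. It appeared with any frequency only away from the plan's figures, for instance with 15 MME steps (27% of significant trials at the design effect). An interval that ends at 0 beside a significant p is an awkward report caused by ties, and 8.4.2 does not plan that interval.

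**Conclusion.** The concern holds as a should-fix. The primary test and effect measure depend on the observed outcome with no stated criterion, the transformable case has no analysis, and 8.4.1 and 8.4.2 conflict on the normal case. None of this depends on simulation. The main damage is an estimand left open, in a trial sized on a difference in means. The inflation of type I error is secondary: none visible under a mechanical rule, and a total of about 6-7% if the analyst may choose among tests.

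The tablet-step result is a further reason not to rely on HL as the headline effect, but it requires oxycodone-only dosing in 5 mg multiples. Under that assumption roughly half of significant trials at the design effect would show an HL limit of exactly 0; with 2.5 MME steps, about 11-14%. All simulated figures also assume two-sided alpha 0.05 and the distribution shapes named above.

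**What to change.** Replace the conditional text in 8.4.2, and align 8.4.1 with it, by one rule such as: *The primary analysis estimates the unpaired between-arm difference in mean total inpatient MME by linear regression on assigned arm with a heteroscedasticity-robust standard error. The difference, its 95% CI and p-value are reported whatever the distribution. The Wilcoxon test and the Hodges-Lehmann between-arm shift are sensitivity analyses.*

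The text should also say how the adjustment triggered by baseline differences in 8.4.3 relates to this analysis; otherwise a second data-dependent choice remains.

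The cost is wording only, and the sample size stands. Near SD 15, power hardly changes (about 0.88-0.94 for the mean comparison, 0.87-0.93 for Wilcoxon). The real downside is that power may be lost if MME proves strongly skewed, as in the 37% versus 56% case. The sponsor can judge that risk now from the shape of the inpatient data behind 8.2, before any trial outcomes are seen.

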2.3.3 Assessment of Potential Risks and Benefits

As described above, potential risks are not more than encountered in usual care after cesarean delivery. Treatment with the TrueRelief device may improve pain control and reduce opioid requirements.

3. Study Design

This is a blinded randomized trial of 134 individuals undergoing a cesarean delivery who are randomized after cesarean to three times use of non-invasive bioelectronic treatment with TrueRelief device or identical appearing sham device for post-cesarean pain management.

The primary endpoint is the total inpatient morphine milligram equivalents used during hospital admission. The primary hypothesis is that three times use of non-invasive bioelectronic treatment with TrueRelief device decreases the total inpatient morphine milligram equivalents used during hospital admission compared to use with identical appearing sham device. Consenting women will be assigned in a 1:1 ratio to one of the two arms using a secure internet based randomization system. Individuals will be followed through 6 weeks postpartum.

4. Objectives and Endpoints

OBJECTIVES	ENDPOINTS		
Primary			
To evaluate whether non-invasive bioelectronic treatment reduces inpatient post-cesarean opioid consumption.	Total inpatient postoperative opioid consumption in morphine milligram equivalents (MME).		
Secondary			
To evaluate whether non-invasive bioelectronic treatment post-cesarean decreases opioid refill prescriptions.	Opioid prescription filled (beyond that prescribed at discharge) between discharge and six weeks postpartum.		
	Total number of opioid prescriptions filled by six weeks postpartum (beyond that prescribed at discharge).		
To evaluate whether non-invasive bioelectronic treatment post-cesarean decreases the total amount of opioid tablets prescribed at discharge.	Number of opioid tablets prescribed at discharge.		
To evaluate whether non-invasive bioelectronic treatment post-cesarean reduces pain intensity pain scores	Pain severity scores (worst, least, average, current) in last 24 hours assessed on the Brief Pain Inventory numeric scale from 0 to 10 at discharge		

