6.2 Measures to Minimize Bias: Randomization and Blinding

Selection bias is minimized by the randomized design. However, adequate concealment of the assignment and a clear definition of the point of randomization are also important. Eligible and consenting women will be randomized by certified research staff using a secure internet based randomization system. Once the randomization program has been run by the staff member and the assignment revealed, the participant will be considered randomized even if the woman reneges. Assignment to device or sham device will be in a 1:1 ratio according to a randomization sequence. The simple urn method will be used to generate the randomization sequences because it provides a high probability of balance in treatment assignments, it is unpredictable, and it allows an explicit randomization analysis to be conducted with relative ease.³⁷

Research staff will be responsible for randomization and for administering the intervention or sham device. Clinicians will be blinded to the patient's group assignment.

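### Section 8.4.2 names a paired t-test for the primary endpoint, but the two arms are independent and the plan defines no pairs

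*Combined protocol and SAP*

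**What the plan says.** Section 8.4.2 splits the primary analysis by the distribution of MME. If MME is not normal, the sentence (broken by a page header) ends: "distributed and cannot be transformed to approximate normality, the Wilcoxon test and the Hodges-Lehmann estimators of the median will be reported". If it is normal: "If normally distributed then paired t-test and mean with standard deviations will be reported".

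Other sections describe independent groups:

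- Section 3: "Consenting women will be assigned in a 1:1 ratio to one of the two arms using a secure internet based randomization system".
- Section 6.2: "Assignment to device or sham device will be in a 1:1 ratio according to a randomization sequence", and "The simple urn method will be used to generate the randomization sequences".
- Section 8.2, on the total of 134: "Resulting in 67 intervention group and 67 participants in control group".
- Section 8.3: "All statistical analyses will be based upon the total cohort of participants randomized into the trial".
- Section 8.4.1: "For normally distributed continuous outcomes, least squares means general linear regression will be used to estimate means and 95% confidence intervals".

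**The concern.** A paired t-test analyses within-pair differences. It needs a rule that links each observation in one arm to exactly one in the other, and it can use only as many women as can be paired. The plan gives no such rule. On the normal branch, the primary p-value would depend on a pairing that someone has to make up, and women without a partner would drop out of an analysis that Section 8.3 says covers everyone randomized.

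Sections 8.4.1 and 8.4.2 also name different methods for the same situation, a normally distributed continuous outcome. Section 8.4.3 adds that analyses will adjust for baseline imbalance in key risk factors, and a paired t-test has no place for covariates.

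What is at stake is whether the confirmatory test is fixed in advance. If it is not, a result near the significance threshold can be moved across it by the choice of pairs.

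**Working it through.** **1. Are there any pairs?** *Between women:* Sections 3 and 6.2 assign individuals one at a time by urn, with no matching. *Within a woman:* the schedule in Section 1.3 records inpatient MME once, at discharge. Section 7.1.2 collects analgesic use after the cesarean through discharge, and no pre-treatment MME is listed. There is no crossover. Neither kind of pair exists.

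**2. The plan's own sample size.** Inputs from Section 8.2: mean 42, target 33.6 (difference 8.4), SD 15, power 90%. Alpha is not stated, so two-sided 5% is assumed.

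n per arm = 2 × (1.960 + 1.2816)² × (15/8.4)² = 67.01

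This matches 67 per arm. Power at 67 per arm is 90.0% by the normal approximation and 89.6% by the t distribution. The arithmetic alone does not show which test was meant. A paired formula with zero correlation has variance of differences 2 × 15² = 450 and gives (1.960 + 1.2816)² × 450/8.4² = 67.01 pairs, the same number. The evidence in Section 8.2 is its wording, which counts two separate groups of participants.

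**3. Will the arms be equal?** The urn favours balance but does not force it. Section 6.2 gives no urn parameters, so two standard versions, UD(0,1) and UD(1,1), were simulated with 100,000 sequences of 134 each. Exactly 67:67 occurred in 12% of trials. The mean difference in arm size was 5.3 and the 95th percentile 14, which is 60:74. At 60:74 a paired test uses 60 pairs and leaves out 134 − 120 = 14 women.

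**4. Why the pairing matters.** With 67 in each arm, the mean difference is the same under every pairing, but its standard error is not. With both sample SDs equal to 15, the paired statistic is the two-sample statistic divided by √(1 − r), where r is the chance correlation produced by the pairing, and the degrees of freedom fall from 132 to 66.

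Take an observed difference of 5.2 MME:

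- Two-sample standard error: 15 × √(2/67) = 2.59. Then t = 5.2/2.59 = 2.01 and p = 0.047.
- Under random pairing, r has SD of about 1/√66 = 0.123, so its central 95% range is about ±0.24.
- The paired t then runs from 2.01/√1.24 = 1.80 to 2.01/√0.76 = 2.30.

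In 5,000 random pairings of one simulated dataset with these summaries, the paired p ran from 0.024 to 0.077 (central 95%), and 53% of pairings were below 0.05.

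**5. Power** (noncentral t, difference 8.4, SD 15, two-sided 5%, zero correlation):

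| Arm sizes | Two-sample t | Paired t |
|---|---|---|
| 67:67 | 89.6% | 89.1% (67 pairs) |
| 60:74 | 89.3% | 85.5% (60 pairs) |
| Averaged over 4,000 urn sequences | 89.5% | 87.8% |

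**6. Stability of the verdict** (100 normal datasets per row at 67:67, 2,000 random pairings each):

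| Two-sample p | Pairings with paired p < 0.05 |
|---|---|
| 0.03 | 95.5% |
| 0.04 | 74% |
| 0.05 | 44% |
| 0.06 | 22% |

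At a two-sample p of 0.03, the central 95% of paired p-values is 0.014 to 0.053.

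**7. Type I error** (20,000 null trials at 67:67). Two-sample test 4.75%, one fixed pairing 4.9%, best of ten pairings 7.3%. With one random pairing, the paired and two-sample verdicts differ in 1.1% of trials under the null and 1.9% under the design effect.

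**The case against.** The strongest reply is that this is a one-word slip. Section 8.4.1, the repeat of its rule for secondary outcomes in 8.4.2, the baseline adjustment in 8.4.3 and the two groups in 8.2 all point to an unpaired analysis, so a reader has a documented fallback. That is probably how the word arose. But the specific sentence on the primary endpoint would normally override the general one. The likely replacements (pooled t, Welch t, adjusted linear model) are also not the same analysis, so the plan still has to name one.

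Second, the re-pairing results and the 7.3% describe something nobody is shown to intend. This is fair. They are hypothetical and show what the text leaves open, not what the investigators would do. The like-for-like figures are the fixed-pairing ones, and those are small.

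Third, the branch may never be used. The non-normal case comes first in 8.4.2, and Section 2.2 says more than 80% of women take an opioid after cesarean, which leaves room for zero values. Against that, the planning mean is 42/15 = 2.8 SDs above zero, and the plan keeps the normal branch. The documents do not settle the matter.

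Fourth, the imbalance figures depend on assumed urn parameters. That is correct, although the two versions tried gave the same 12%. The lack of pairs does not depend on them.

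**Conclusion.** The concern holds. On the normal branch, the stated primary test does not fit the design, conflicts with Sections 8.3 and 8.4.1, and cannot be carried out without a pairing rule that the plan does not contain. It should be fixed, but it does not threaten the trial. The sample size is unaffected. With a pairing fixed blind to outcome, type I error stays near 5%, and power falls by 0.5 percentage points at 67:67 and by 1.7 on average over urn imbalance (89.5% − 87.8%). The real harm is a primary p-value that is not defined in advance and can cross 0.05 with the choice of pairs, with false positives inflated if that choice is made after seeing the data. The non-normal branch does not share the defect.

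The figures assume normal data, SD 15 in both arms, no missing outcomes, a two-sided 5% level and standard urn parameters. The finding that no pairs exist needs none of these.

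**What to change.** In Section 8.4.2, replace the paired t-test with one named independent-groups analysis: a two-sample t-test (stating pooled or Welch) or the linear model of Section 8.4.1. Report the difference in means with its 95% confidence interval, beside the arm means and SDs.

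For clarity in the same sentence, name the non-normal alternative as the Wilcoxon rank-sum test with the two-sample Hodges-Lehmann shift and its confidence interval. Next to the word paired, an unqualified Wilcoxon test could be read as signed-rank.

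This costs a wording change in 8.4.2, with no new data and no extra participants.

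A separate and smaller point for Sections 8.1 and 8.2 is to state the primary alpha and sidedness. The alternative in 8.1 is directional. Two-sided 5% and one-sided 2.5% both give 67.01 per arm, whereas one-sided 5% gives 2 × (1.645 + 1.2816)² × (15/8.4)² = 54.6 and does not reproduce 134.

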8.4.3 Baseline Descriptive Statistics

Baseline factors will be compared by treatment group. If the treatment groups are found to differ on a key pre-treatment factor known to be a risk factor for the outcome, the statistical analyses will adjust for these differences.

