7.1.2 Baseline Procedures

If the patient is eligible and signs the consent form, participants be randomized to TrueRelief device or identical appearing sham device:

In addition to information collected for eligibility, the following information will be obtained from an interview with the participant and/or through the electronic medical record:

- Demographic factors (e.g., maternal date of birth, age, BMI, race/ethnicity, education, employment status, marital status, household income, insurance)
- Factors related to persistent opioid use including tobacco use, history of mental health conditions (e.g., depression, anxiety), use of anti-depressants or benzodiazepines, chronic pain conditions (e.g., back pain, migraines, fibromyalgia).

Medical history including obstetrical outcomes from the current delivery (e.g., indication for cesarean, repeat cesarean, labor prior to cesarean, operative time, type of anesthesia, perioperative complications, gestational age, birth weight, neonatal outcomes).

• Opioid and non-opioid analgesics (e.g., acetaminophen, ibuprofen) use post cesarean through discharge

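### Covariate adjustment hinges on an undefined baseline imbalance (8.4.3), so the primary model is not fixed before baseline data by arm are seen; adjusting by a fixed list would be more efficient if the factors are prognostic

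*Combined protocol and SAP*

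**What the plan says.** Section 8.4.3 compares baseline factors by arm and sets a condition: "If the treatment groups are found to differ on a key pre-treatment factor known to be a risk factor for the outcome". When it is met, "the statistical analyses will adjust for these differences". No test, threshold or size of difference is given, no factors are listed, and no endpoint is excluded.

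For total inpatient MME, section 8.4.2 gives two paths. If the data are not normal and cannot be transformed, "the Wilcoxon test and the Hodges-Lehmann estimators of the median will be reported". Otherwise, "If normally distributed then paired t-test and mean with standard deviations will be reported". Neither carries covariates. (The arms are independent, so the t-test is read here as a two-sample test.) For normally distributed continuous outcomes in general, section 8.4.1 says "least squares means general linear regression will be used to estimate means and 95% confidence intervals", again without naming covariates.

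On allocation, section 6.2 says "The simple urn method will be used to generate the randomization sequences" and names no stratification factor. Section 7.1.2 already collects candidate factors, including "repeat cesarean, labor prior to cesarean, operative time, type of anesthesia" and chronic pain conditions. Labor and primary versus repeat cesarean reappear as subgroup factors under section 8.4.4.

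**The concern.** In a randomized trial a baseline difference between arms is a chance event, so its observed size is a poor guide to whether a factor belongs in the model. What matters is whether the factor predicts the outcome. A rule triggered by imbalance has two consequences.

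- **The primary model is not fixed in advance.** Two analysts could read the same baseline table, define *differ* or *key* differently, and fit different primary models. On the Wilcoxon path, a triggered adjustment has no specified method at all.
- **Efficiency is lost if the factors are prognostic.** Adjustment improves precision whether or not the arms happen to differ, and the rule uses it only when they do.

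Because allocation is not stratified, the design does not itself limit imbalance on these factors.

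**Working it through.** **1. The plan's sample size.** Section 8.2 gives mean 42, SD 15, a reduction to 33.6 (difference 8.4), 90% power and 134 in total. No alpha is stated for the primary endpoint; two-sided 0.05 is assumed.

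n per arm = 2 × (1.960 + 1.282)² × (15/8.4)² ≈ 67.01, or about 134 in total, so the figure reproduces as an unadjusted two-sample comparison. Power at 67 per arm is 90.0% by the normal formula and 89.6% by the t formula.

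**2. How often the rule would adjust.** Assume three independent yes/no factors with prevalence 50%, 50% and 20%.
- Reading *differ* as p<0.05: 1 − 0.95³ = 14.3%; simulated 13–14%.
- Reading it as 10 percentage points or more: simulated 53–55%. (One 50% factor alone: 26.1%, exact binomial.)
- With ten factors, all at 50% prevalence, the rates are 38% and 95%.

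**3. What fixed adjustment can offer.** The adjusted standard error is about 15 × √(1 − R²) × √(2/67). At R² 0.20 this is 13.42 × 0.1728 = 2.32. Then 8.4/2.32 − 1.96 ≈ 1.66, or 95.2% power. The documents give no R², so a range is shown.

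**4. Simulated power on the normal path (%).** 67 per arm, difference 8.4, SD 15, the three factors above with equal shares of R², 20,000 trials per cell. Under the triggers, only the differing factors are adjusted for. Simulation error per entry is about √(0.9 × 0.1/20,000) = 0.2 point.

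| R² | Unadjusted | Trigger p<0.05 | Trigger 10 points | Fixed adjustment |
|---|---|---|---|---|
| 0 | 89.6 | 89.4 | 89.1 | 88.9 |
| 0.05 | 89.9 | 90.0 | 89.9 | 90.6 |
| 0.10 | 89.4 | 89.6 | 90.4 | 91.7 |
| 0.20 | 89.5 | 90.1 | 91.4 | 94.5 |
| 0.30 | 89.5 | 90.5 | 92.7 | 96.4 |

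Fixed adjustment costs 89.6 − 88.9 = 0.7 point at R² 0. It gains 2.3, 5.0 and 6.9 points at R² 0.10, 0.20 and 0.30.

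**5. Share of the gain that the rule keeps, R² 0.10–0.30.**
- Power, p<0.05 trigger: 0.2/2.3, 0.6/5.0 and 1.0/6.9, or about 9–14%.
- Power, 10-point trigger: 1.0/2.3, 1.9/5.0 and 3.2/6.9, or about 38–46%.
- Variance of the estimate: about 24–33% of the reduction is kept with p<0.05, and about 61–72% with 10 points.

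**6. Error rate and conclusions.** Type I error is 4.3–5.0% under the p<0.05 trigger and 3.5–5.0% under the 10-point trigger. With a true effect, the two readings reach different 5% conclusions in 0.9–3.9% of trials.

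**7. Wilcoxon path.** With skewed MME (assumed gamma, shape 2; 6,000 trials per cell), a van Elteren test stratified by labor was compared with the plain Wilcoxon. If labor carries one third of R², power is 96.5 vs 96.5, 95.7 vs 95.6, 95.9 vs 95.2, 95.5 vs 93.2 and 94.8 vs 92.2% at R² 0, 0.05, 0.10, 0.20 and 0.30. If labor carries all of R², it is 97.5 vs 94.6% at 0.10 and 99.3 vs 91.6% at 0.30. The largest loss seen was 0.3 point (95.6 vs 95.9%, R² 0, MME rounded to steps of 7.5).

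**The case against.** The strongest reply is that section 8.4.2 is the section on the primary endpoint and names its tests, while 8.4.3 sits under baseline descriptive statistics and never mentions that endpoint. On that reading the primary test is unadjusted and adjustment is supportive. Section 8.4.3 also limits itself to pre-treatment factors known to be risk factors, and 8.4.1 names a regression that can carry covariates. This reading is natural, but no sentence states it, and the wording of 8.4.3 covers the statistical analyses without exception. The ambiguity stands.

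The second reply is that the harm is small and the gain assumed. This largely stands. R², the prevalences and the independence of the factors are not in the documents. No section says that these factors predict inpatient MME, and 7.1.2 lists chronic pain under persistent opioid use. If R² is zero, fixed adjustment costs power.

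A reader might infer that the rule throws away most of the available precision. That holds in variance terms only under the p<0.05 reading; under the 10-point reading about two thirds of the variance reduction is kept. If a triggered trial adjusted for all three factors rather than only those that differ, the 10-point reading would keep 80–83% of the variance reduction and 64–70% of the power gain.

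**Conclusion.** The point holds as a defect of specification with a moderate efficiency cost. The primary model depends on two undefined words until baseline data by arm are seen, and the plan does not say which result is primary.

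At assumed R² of 0.10–0.30, fixed adjustment gives about 92–96% power, against 90–91% with a p<0.05 trigger and 90–93% with a 10-point trigger. Less than half of the power gain is kept under either trigger when only the differing factors enter the model. These sizes rest on the assumed R², prevalences, independence and triggers.

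Two stronger inferences are not supported. The rule does not make the trial underpowered: power stays near 90%. Nor does it inflate type I error when followed mechanically, because it looks only at baseline factors. Taking the better of the adjusted and unadjusted results would raise type I error to 5.6–7.5%, but nothing in the plan authorizes that choice. The change is worth making, but the trial's validity does not turn on it.

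**What to change.** - Delete the conditional sentence in 8.4.3 and keep the baseline table descriptive.
- Before data by arm are seen, name a short set of pre-treatment covariates already collected under 7.1.2, to be used whatever the observed balance. One example is labor before cesarean, primary versus repeat cesarean, and chronic pain condition (yes/no). The choice is a judgment, since 8.4.4 lists other candidates such as BMI category and neuraxial morphine. If the inpatient data reviewed for 8.2 record these factors, use them to confirm it.
- Normal path: make linear regression on arm plus these covariates primary, using the method already named in 8.4.1.
- Wilcoxon path: make a van Elteren test stratified by one pre-named factor primary, with a Hodges-Lehmann shift from within-stratum differences. Robust regression is not proposed here: at R² 0–0.10 it had 89–92% power in the skewed simulation, below the Wilcoxon, although it overtook the Wilcoxon at 0.20 and above.
- Report the unadjusted result as a sensitivity analysis.
- State in advance the criterion for choosing the path and the effect scale to be reported, including after any transformation, since 8.2 plans in MME units. Without this, the choice of path still depends on outcome data.

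The cost is a rewritten paragraph in each of 8.4.2 and 8.4.3, with no added participants, visits or data items. If the covariates predict nothing, the power cost is about 0.7 point on the normal path and at most 0.3 point on the Wilcoxon path in the simulations. The gain is not assured.
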